1. PROTOCOL SUMMARY

Protocol Title	ENDObesity II Study: Endoscopic Treatment for Weight Reduction in Patients with Obesity Using the TransPyloric Shuttle® System: A Multicenter, Prospective, Randomized, Double-blind, Sham-controlled, Parallel-design Study
Protocol Number	DTC006
Investigational Device	TransPyloric Shuttle® System (TPSS)
Proposed Indication	The TransPyloric Shuttle System is indicated for weight reduction in patients with obesity with a Body Mass Index (BMI) of 35.0-40.0 kg/m ² or a BMI of 30.0 to 34.9 kg/m ² with one or more obesity-related comorbid conditions.
Regulatory Status	The device is under clinical investigation in the US for the proposed indication stated above.
Objectives	The objective of this study is to assess the safety and effectiveness of the TransPyloric Shuttle (TPS®) for weight reduction in obese subjects with BMIs of 30-40 kg/m ² .
Study Design	
This is a multicenter, prospective, randomized, double-blind, sham-controlled, parallel-design study conducted in the United States.
 
The pivotal study cohort will consist of 270 pre-planned study subjects which will be randomized in 2:1 ratio to the Treatment or the Control group from up to 12 sites. Subjects who sign the informed consent and are deemed eligible following a general and endoscopic screening will be enrolled in the study and randomized.
 
Subjects assigned to the Treatment group will receive the TPS placement and the subjects in the Control group will undergo a sham procedure without TPS placement. The subjects will be blinded to their treatment. The Investigators and/or study coordinators who collect the primary outcome data will be masked to subjects' treatments.
 
Subjects will be followed for 12 months or less than 12 months if the subject achieves the midpoint of the normal BMI range (22 kg/m²), at which time the subject is considered to have completed the study and the device removed if the subject had received the TPS device.
 
Subjects will receive brief (15 minute) lifestyle-modification counseling sessions at each follow up visit. They also will receive brief (15min) telephone calls in the months that do not include in person visits between 6 and 12 months (in months 7, 8, 10, and 11). These counseling sessions are centrally designed to improve adherence to recommendations to consume a healthy diet and increase physical activity to promote weight loss and overall health. The counseling sessions and telephone calls will be provided by a member of the research team (dietitian, nurse, etc.) trained in the delivery of the prescribed lifestyle counseling.

Patient Population	Male and female subjects, 22-60 years of age, with a BMI of 35.0 to 40.0 kg/m ² , inclusive, or a BMI of 30.0 to 34.9 kg/m ² with at least one obesity-related comorbidity.

Co-Primary Endpoints
	
 • Mean percent total body weight loss (% TBL) between the Treatment and the Control group at 12 months after the index procedure. • The proportion of subjects in the Treatment group who achieve $\geq 5\%$ TBL at 12 months after the index procedure.

Secondary Endpoints
	
 • Proportion of subjects who achieve at least 7% and 10% TBL at 12 months in the Treatment versus Control group • Percent total body weight loss over 12 months in the Treatment versus Control group • Percent excess weight loss over 12 months in the Treatment versus Control group • Proportion of subjects who achieve at least one obesity class reduction at 12 months in the Treatment versus Control group • Change of BMI over 12 months from baseline in the Treatment group • Change in weight-related quality of life over 12 months as assessed by IWQOL-Lite Questionnaire • Change in eating behavior over 12 months as assessed by the Eating Inventory • Change in appetite, hunger and fullness over 12 months as assessed by Visual Analog Scales • Change in comorbid conditions over 12 months in the Treatment group: 
 ○ Prevalence of the metabolic syndrome and its individual components ○ Glucose, insulin, and insulin resistance (as estimated by HOMA) ○ High sensitivity C-reactive protein (hsCRP) ○ Lipid levels (LDL-C, HDL-C, and triglycerides) ○ Blood pressure ○ Waist circumference

Safety Evaluation
	
Safety will be characterized through a summary of the incidence of adverse events. A Clinical Event Committee (CEC) will review and adjudicate all serious device-related adverse events and any other events deemed necessary.

Key Inclusion Criteria
	
 1. Male and female subjects between the ages of 22 to 60 2. A BMI between 30.0 to 40.0 kg/m² inclusive. Subjects with a BMI of 30.0 kg/m² to 34.9 kg/m² are required to have one or more of the following obesity-related mild-moderate comorbidities: 
 a. Type 2 Diabetes: meet one of the following criteria and currently not using insulin 
 i. HbA1c 6.5%-7.5% ii. Controlled, on stable dose of oral medications for at least 3 months b. Hypertension, meet one of the following criteria: 
 i. Arterial blood pressure >140 mmHg systolic or >90 mmHg diastolic on or off hypertensive medication ii. Arterial blood pressure ≤ 140 mmHg systolic and ≤ 90 mmHg diastolic on hypertensive medication c. Hyperlipidemia, meeting at least one of the following criteria: 
 i. Fasting blood total cholesterol level of ≥ 240 mg/dl ii. Fasting total triglyceride level of ≥ 200 mg/dl

	
 iii. Low density Lipoprotein cholesterol ≥ 160mg/dl iv. Currently taking lipid-lowering medication based on an elevation of total cholesterol, triglycerides, or LDL 3. History of obesity for at least 2 years, with history of failure of medically or commercially supervised weight loss program 4. History of weight stability (defined as a < 5% change in body weight) for at least 3 months prior to the screening visit 5. Female subjects of childbearing potential must have a negative urine pregnancy test and must commit to practice their physician-agreed form of birth control for the duration of participation 6. Willing and able to provide written informed consent 7. Willing and able to comply with study procedures and return for all study visits

Key Exclusion Criteria
	
 1. Pregnancy or planned pregnancy in next 12 months after enrollment 2. Nursing or pregnancy within the 6 months prior to enrollment 3. Known hormonal or genetic cause for obesity 4. Prior history of any surgery or endoscopic intervention that has altered esophageal, gastric or duodenal anatomy, including any bariatric surgery, such as gastric bypass, and restrictive procedures such as laparoscopic adjustable gastric banding 5. Prior treatment with an intragastric balloon for the purpose of weight loss, where the balloon was removed less than 12 month prior to the screening visit for this study 6. Chronic use (at least past 6 months) of medications likely to contribute to weight gain or prevent weight loss (e.g., corticosteroids, lithium, olanzapine, risperidone, clozapine, anticonvulsants, glitazones (e.g., pioglitazone), monoamine oxidase inhibitors) 7. A history of gastric or duodenal ulcers 8. After treatment for Helicobacter pylori, subject still tests positive for H. pylori 9. A history of severe dyspepsia 10. GI tract motility disorders such as esophageal motility disorders, gastroparesis diabeticorum, or intractable constipation 11. History of inflammatory disease of GI tract, such as Crohn’s disease 12. History of coeliac disease 13. History of pancreatitis 14. History of portal hypertension, cirrhosis, and/or varices 15. Diabetes treated with insulin or significant likelihood of requiring insulin in next 12 months 16. HbA1c >7.5% 17. Uncontrolled thyroid and adrenal gland disease 18. Uncontrolled hypertension defined as systolic blood pressure > 160 mmHg or diastolic blood pressure > 100 mmHg 19. A history of cardiac arrhythmia, ischemic heart disease, myocardial infarction or chronic heart failure 20. History of cerebrovascular disease, transient ischemic attack, or stroke 21. Presence of localized or systemic infection 22. Anemia (hemoglobin <11.0 g/dl for female and <12.0 g/dl for male)

	
 23. History of asthma likely to require systemic steroid therapy during the duration of the study participation or frequent use of rescue inhalers 24. Autoimmune connective tissue disorders or known to be immunocompromised or at risk of becoming immunocompromised (e.g., HIV positive) 25. A history of malignancy except non-melanoma skin cancer 26. Continuous therapy with known ulcerogenic medication (e.g., aspirin greater than 81mg/day, NSAIDs) 27. On anticoagulation or antiplatelet therapy (e.g., Coumadin, Warfarin, Heparin, Pradaxa, Xarelto, Plavix) 28. Unwilling to avoid use of any weight-loss medication, including over-the-counter treatments and/or herbal supplements, during the course of study, or on prescription medications that can be used for weight loss, even if they are not prescribed for weight loss (e.g., Topiramate, Wellbutrin) and stimulant medications (e.g., for ADHD) 29. Currently participating, or unwilling to avoid participation in any non-study-related organized weight-loss program (medical or commercial) during the course of the study 30. Unable to take proton pump inhibitor (a daily 40+mg of Omeprazole or equivalent), or addition of PPI may cause adverse drug interaction with subject's medication or interruption of treatment 31. Clinically significant abnormal laboratory values or an EKG that make the subject a poor study candidate in the opinion of the Investigator 32. Inability to walk at least 0.8 kilometers per day (10 minutes of continuous walking) 33. Planned surgical procedure that can impact the conduct of the study 34. Started on a prescribed medication regimen within the last three weeks, or whose concomitant medication regimen is expected to change during the course of the study, and where the Investigator determines the medication may affect the study outcome 35. Known allergy to any component materials in the TPSS such as silicone, barium sulfate, parylene 36. Current smoker or user of nicotine product or smoking cessation within 1 year of the screening date 37. Current abuse of drug or alcohol or past treatment for substance abuse 38. Presence of any severe, uncontrolled psychiatric illness 39. Inpatient psychiatric treatment within the past year 40. A score of ≥ 10 on the Patient Health Questionnaire 9 (PHQ-9), indicating moderate depression 41. Diagnosis of bulimia nervosa or binge eating disorder 42. Any medical condition (including psychiatric disease) that would interfere with the interpretation of the study results, the conduct of the study, or would not be in the best interest of the subject in the opinion of the site Primary Investigator. 43. Participation in another clinical study within 60 days of screening date, in previous or ongoing clinical study, or plan to participate in another clinical study at any time during this study
--	--

	
44. Employee or family member of BAROnova, the Investigator, or site study staff
 
45. The Investigator judges the candidate unsuitable for the study
 
46. Have any of the following endoscopic exclusion criteria
 
 a. Esophageal stricture b. Barrett’s esophagus c. Erosive esophagitis d. Varices e. Angiectasias f. Gastric mass g. Antral or peri-pyloric polyps h. Peptic ulceration i. Hiatal hernia \geq 4 cm j. Pyloric stricture k. Any other abnormalities/characteristics that would preclude safe use of the TPS
Post Procedure Follow-up and Assessment Schedule	
 • Office visits: 1 week, and 1, 2, 4, 6, 9, and 12 month(s) • Endoscopic follow up [REDACTED] • Blood tests: 6 and 12 months • Eating Inventory and Visual Analog Scales: 1 week, and 1, 6, 12 months • IWQOL-Lite: 6 and 12 months • Device removal: 12 months
Analysis Population	
Intent-to-Treat: includes all randomized and enrolled subjects regardless of whether or not the subject receives the randomized treatment.
 
Per -Protocol: includes all subjects who receive the assigned treatment and do not have any major eligibility violations.
 
Modified Intent-to-Treat: consists of the Intent-to-Treat population that have received the assigned treatment and have at least one post-treatment follow up, including the index procedure visit.
 
Completed Cases: includes all enrolled subjects who have the 12-month follow-up visit, or have completed the study based on reaching the BMI objective of \leq 22 kg / m² in two consecutive follow-up visits as described in Section 5.1.

Proton Pump Inhibitor (PPI) Use	
Subject will be placed on PPI (Omeprazole 40 mg daily or equivalent) starting at least one week before the index procedure and continue until the TPS removal (or the last visit in the Control subjects).

Post Procedure Patient Management	
 • Subject will be on a liquid diet for 3 days, followed by soft food for 7 days, and then a normal diet. • Subject will have antiemetic and antispasmodic on standby.
Safety Monitoring	
Safety will be monitored throughout the study. The Investigators will assess the occurrence of adverse events at each follow up visit. The Data Safety Monitoring Board (DSMB) will monitor and evaluate the safety data throughout the study. A pre-specified staged safety monitoring will be performed after the first 30, 60 and 90 subjects in the Treatment group have reached 80 days post index procedure.

Timeline	
 • First Subject Enrolled: Q4 2015 • Estimated Enrollment Duration: 12 months (Q4 2016) • Last Subject to Primary Endpoint Follow-up: (Q4 2017)

	
• Study Duration: 24 months
--	---

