6.3. Safety Evaluations

The overall device safety profile is characterized by assessing the incidence of adverse events (AEs), serious adverse events (SAEs), serious adverse device effects (SADEs), and unanticipated serious adverse device effects (UADEs) as detailed in Section 12. No formal hypothesis testing will be performed.

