7.5. Patient Discontinuation

Once enrolled, each subject will remain in the study until the required follow-up period is complete. However, the subject has the right to withdraw from the study at any time without penalty or loss of benefit. The following events will result in terminating the subject's follow-up:

- Subject voluntary withdrawal
- Subject withdrawn by the Investigator as clinically indicated
- Subject becomes pregnant
- Subject lost to follow-up
- Subject death
- Study is terminated according to Section 5.6 (Early Study Termination)

In the case of subject withdrawal from the study, the TPS must be removed before the subject exits the study.

In case the TPS is removed early as described in Section 10.5, the subject's participation in the study is considered terminated. Any Adverse Events will be followed until resolution or stabilization according to Section 12.1.

In case a subject achieves normal BMI (≤ 22 kg/m²) for two consecutive visits before the 12-month follow up, the subject is considered to have completed the study. Subject will exit the study and the device should be removed in the treatment subjects.

A final endoscopy should be performed whenever possible before the Treatment subject exits the study.

The Sponsor must be notified of the reason for subject discontinuation. The site will document this information on the electronic case report form (eCRF) and make every effort to give a full description of the reason for withdrawal. Investigators must also report this information to the local IRB as defined by their institution's procedure.

Subjects who are terminated early will not be replaced by enrolling additional subjects.

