15.2. Analysis Populations

The following analysis populations are defined for the study: Intent-to-Treat (ITT), modified Intent-to-Treat (mITT), Per-Protocol (PP) and Completed Cases (CC). The primary effectiveness hypotheses will be tested on the PP population. The primary safety analysis will be performed on mITT population. The ITT and CC populations will be used in a sensitivity analysis of the primary effectiveness endpoint.

- Intent-to-Treat: The Intent-to-Treat population includes all randomized and enrolled subjects as defined in Section 7.4 regardless of whether or not the subject received the randomized treatment.
- Per-Protocol: The Per-Protocol population is a subset of the ITT population and includes all subjects who receive the assigned treatment and do not have any major eligibility violations.

- **Modified Intent-to-Treat:** The mITT population consists of the ITT population subjects who received the assigned treatment and that have at least one post-treatment follow-up, including the index procedure visit.
- **Completed Cases:** The CC population includes all enrolled subjects who have the 12-month follow-up visit, or have completed the study based on reaching the BMI objective of $\leq 22 \text{ kg} / \text{m}^2$ in two consecutive follow-up visits as described in Section 5.1.

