15.4. Sample Size Considerations

A total sample size of 270 subjects is planned for the pivotal study cohort. The ENDObesity I study provided estimates for the mean %TBL of 14.5 (SD=5.8) at 6 months of follow-up. For the purposes of the sample size calculation, the assumed means were 13% in Treatment and 5% in Control subjects. This provides a difference (Treatment – Sham Control) in mean %TBL of 8% and the assumed standard deviation was increased to 9% (approximately 1.5 times that observed in the ENDObesity I study) to account for a more conservative estimate of the standard deviation. Under these assumptions, a sample size of 243 subjects (162 Treatment, 81 Control) has 90% power to reject H_0 under the 4% superiority margin scenario and 68.4% power under the superiority margin of 5%. Under less conservative scenario of standard deviation of 7, the study has 88% power to reject H_0 under the 5% superiority margin scenario and 99% power under the 4% superiority margin. The study will enroll 270 subjects (approximately 180 in the Treatment groups and 90 in the Control group) to compensate for losses to follow-up.

The second co-primary endpoint is to demonstrate the proportion of subjects with a $\geq 5\%$ TBL at 12 months is greater than 50%. Under the assumption of 65% responder rate in the Treatment group, the study requires 113 treatment subjects in order to have 90% power to reject null hypothesis for the second co-primary endpoint.

A third consideration for the sample size is the ability to provide reasonable safety data from the study. With the proposed sample size of 180 subjects in the Treatment group, there is an 80% likelihood to observe at least one event of any specific complication if it occurs in at a rate of 0.9% or greater in subjects treated with the TPSS. The upper limit of 95% exact binomial confidence interval for an event rate if none of 180 subjects has specific complication is 2.0%.

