15.5.5. Safety Analysis

The safety analyses will be performed using the mITT Population.

An overall summary of AEs will be provided including the number of events and percent of subjects with any AEs, SAEs, and UADEs. For each type of event, the number of events and number and percent of subjects with the event will be provided in a table. Separate summaries of all adverse events will be summarized by relationship to device and procedure. Adverse events will be coded using MedDRA medical dictionary.

15.5.6. [REDACTED]

[REDACTED]

[REDACTED]

[REDACTED]

[REDACTED]

[REDACTED]

[REDACTED]

[Redacted]

15.5.7. [Redacted]

[Redacted]

[Redacted]

[Redacted]

[Redacted]

[Redacted]

[Redacted]

[Redacted]

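### The visible adverse event summary is a crude percent of treated subjects with no time at risk, so late-residence complications are modestly understated when subjects exit early

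*Combined protocol and SAP*

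**What the plan says.** The Protocol Summary sets the aim: "Safety will be characterized through a summary of the incidence of adverse events". Section 6.3 makes safety descriptive: "No formal hypothesis testing will be performed". Section 15.5.5 sets the population, "The safety analyses will be performed using the mITT Population", and the measure: for each type of event, "the number of events and number and percent of subjects with the event will be provided in a table". Section 15.2 defines mITT subjects as those who "received the assigned treatment and that have at least one post-treatment follow-up, including the index procedure visit", so anyone treated who has the index visit stays in the denominator.

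Section 7.5 deals with early removal: the subject's "participation in the study is considered terminated". Adverse events already present are followed to resolution or stabilization. Section 11.9.10.1 leaves follow-up after study exit to clinical practice. Section 10.5 applies the same exit rules to Control subjects, as if they carried the device.

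Section 15.4 computes efficacy power on 162 Treatment and 81 Control subjects, and enrols about 180 and 90 to allow for losses. Its safety figures use all 180: an 80% chance of seeing at least one event with a true rate of 0.9%, and "The upper limit of 95% exact binomial confidence interval for an event rate if none of 180 subjects has specific complication is 2.0" percent.

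Sections 15.5.6 and 15.5.7 are redacted. Appendix A lists K-M as an acronym, but no visible analysis uses it.

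**The concern.** A percent of treated subjects equals the 12-month risk only if all are observed for 12 months or all events come early. Here observation of new events stops at removal or exit, and the denominator does not change. A low count of late events could mean few complications, or few devices still in place, and the visible tables would not tell these apart.

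The time lost is the time with least prior information. In the feasibility study the device stayed in for 3 months in 10 subjects and 6 months in 10 subjects (Sections 3.4.1 and 3.4.3). This study keeps it in for 12 months, and Section 7.6 acknowledges that the long-term response of its materials in the stomach is unknown.

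Benefit and harm are also handled differently. Missing follow-up weights are multiply imputed (Section 15.5.3), while adverse events are counted only up to exit. Section 12 then weighs the one against the other.

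**Working it through.** **1. The plan's own safety figures (Section 15.4), n = 180.**
- Chance of at least one event at 0.9%: 1 − 0.991^180 = 80.35% (stated 80%).
- Rate detectable with 80% probability: 1 − 0.2^(1/180) = 0.89% (stated 0.9%).
- Two-sided 95% exact upper limit for 0 of 180: 1 − 0.025^(1/180) = 2.03% (stated 2.0%).

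All three reproduce.

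**2. Implied loss.** 1 − 162/180 = 10%. The plan does not state this percentage; it follows from the two sample sizes.

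**3. Crude percent against risk under full residence.** Let R be the true 12-month risk if everyone were observed, and d the proportion exiting by 12 months at a constant rate unrelated to event risk. Put h = −ln(1 − R) and c = −ln(1 − d).

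- Constant event hazard: crude = h/(h + c) × [1 − (1 − R)(1 − d)].
  For R = 5%, d = 10%: h = 0.0513, c = 0.1054, so 0.0513/0.1567 × (1 − 0.855) = 4.75%.
- All risk in months 6-12: crude = √(1 − d) × h/(h + c/2) × [1 − (1 − R)√(1 − d)].
  For R = 5%, d = 10%: 0.9487 × 0.0513/0.1040 × (1 − 0.9012) = 4.62%.
- All risk in month 1: obtained by numerical integration.

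Observed crude percent when the true 12-month risk is 5%:

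| Exit by 12 months | All risk in month 1 | Constant hazard | All risk in months 6-12 |
|---|---|---|---|
| 10% (implied by 15.4) | 4.98% | 4.75% | 4.62% |
| 20% (assumed) | 4.95% | 4.49% | 4.23% |
| 30% (assumed) | 4.93% | 4.21% | 3.83% |

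Relative shortfall at 10% exit: (5 − 4.75)/5 = 5%, and (5 − 4.62)/5 = 7.6%. For a true 10% risk at 10% exit, the crude values are 9.50% (constant) and 9.25% (late), again 5% and about 8%. Early events are almost unaffected.

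**4. Section 15.4 for complications that need long residence.**

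| Treatment subjects | Chance of seeing a 0.9% event | Rate detectable at 80% | Upper limit, zero events |
|---|---|---|---|
| 180 (all treated) | 80.4% | 0.89% | 2.03% |
| 171 (10% loss spread evenly: (180 + 162)/2) | 78.7% | 0.94% | 2.13% |
| 162 (observed throughout) | 76.9% | 0.99% | 2.25% |

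**The case against.** **The size is small.** At 10% exit and a true 10% risk with constant hazard, the shift is 0.5 points against a standard error of √(0.1 × 0.9/180) = 2.2 points. For a true 5% late risk it is 0.38 points against √(0.05 × 0.95/180) = 1.6 points. Each is about a quarter of a standard error. This stands. The larger shortfalls in the table need assumed exit rates. The case for change rests mainly on months 6-12 being unreadable without numbers at risk.

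**The method may be in redacted text.** Section 14 ties 15.5.6 to staged safety monitoring, which the Protocol Summary sets at 80 days after the procedure. A method there would probably not cover months 6-12. The content of 15.5.7 is unknown, and the otherwise unused K-M acronym is suggestive. A reader might infer that the plan has no time-to-event safety analysis; the documents support that only for the visible text.

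**Other provisions cover it.** Section 15.1 allows summaries by visit where appropriate, Section 15.5.1 reports withdrawals with reasons, and the DSMB reviews cumulative safety data (Section 14). None of these puts time at risk beside the event counts.

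**The crude percent is valid for what it describes.** It gives the incidence observed under the protocol's removal rules, and an event that prompts removal is already counted. This is correct, and is why the crude table should stay.

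**Arm bias.** A reader might infer that exposure is shorter in the Treatment arm by design, so that the comparison favours the device. The documents do not establish this. Control subjects follow the same exit rules, and withdrawal or loss could be higher in either arm. Imbalance is plausible, because several removal triggers in Section 10.5 concern ulcers and the expected effects of residence include ulceration and early removal (Section 3.5.2).

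**Conclusion.** The point holds for the visible text of Section 15.5.5. Crude percents of mITT subjects understate the 12-month risk under full residence for complications that arise evenly or late, by about 5-8% in relative terms at the implied 10% loss and by more if exits are more frequent. This assumes exit spread over the year and unrelated to event risk. Removal for ulcer or pain probably breaks the second assumption, so the figures indicate scale and are not a correction to apply.

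Two further readings should be resisted. Section 15.4 is not in error: its figures reproduce, and 180 matches the safety set. Nor does the plan say that 162 Treatment subjects are expected to complete. That is an inference from the loss allowance, and subjects who leave early still contribute exposure, so at that loss rate 162 is the least favourable count.

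**What to change.** Keep the crude table in Section 15.5.5 and add one table for device-related events, SAEs and ulcers, by arm and separately for months 0-6 and 6-12:

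- number at risk at the start of each period;
- subject-months from index procedure to removal or exit;
- events per 100 subject-months;
- cumulative incidence to 12 months, with early removal (and the matching Control exits under Section 10.5) as a competing event and loss to follow-up as censoring.

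State what each measure answers. The period rates describe risk while under observation with the device in place. The cumulative incidence gives the probability of the event under the protocol's own removal rules, adjusted only for loss. A Kaplan-Meier curve censored at removal should not replace it, because removal for ulcer or pain carries information about risk. If 15.5.6 or 15.5.7 already provides this, a cross-reference in 15.5.5 is enough.

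In Section 15.4, leave 0.9% and 2.0% as they are. Optionally add that for complications needing full 12-month residence they become about 1.0% and 2.3% if only 162 are observed throughout, or 0.94% and 2.13% if the loss is spread evenly.

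The cost is SAP wording and one table. Onset dates are collected (Section 12.1), and discontinuation and exit are documented (Sections 7.5 and 11.9.10.1). The downside is slightly less favourable late-event figures.
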